Significance: There is an acute and immediate need for the development of safe, effective, and non-habit forming pharmacological treatments for chronic pain disorders. Very large numbers of OEF/OIF Veterans report chronic pain symptoms (as many as 50% or higher). Current medications such as opiates that are frequently used to treat chronic pain symptoms have side effect risks such as respiratory depression, addiction, sedation, and potentially lethal interactions with other drugs. The proposed projects could lead to new therapeutic avenues that are safe, non-habit-forming, and effective. Neurosteroids demonstrate pronounced analgesic actions, and preclinical and clinical data suggest that these molecules hold promise for chronic pain disorders. New agents for the treatment of chronic pain could markedly improve long-term outcome and quality of life in OEF/OIF Veterans.

Relevance to Veteran Health: There is currently a paucity of safe and effective agents for the treatment of chronic low back pain, a disorder that impacts large numbers of OEF/OIF Veterans and is frequently accompanied by PTSD and other comorbid symptoms. Pregnenolone may represent an effective, safe, well-tolerated, immediately accessible, and inexpensive treatment for these symptom domains, potentially leading to improved functional outcome and quality of life in OEF/OIF Veterans with chronic pain disorders.

RESEARCH DESIGN AND METHODS

The proposed randomized controlled trial (RCT) will investigate adjunctive pregnenolone as a potential analgesic in OEF/OIF Veterans with chronic low back pain. This will be a 4-week, randomized, double-blind placebo-controlled pilot study preceded by a one-week placebo lead-in period (all participants). Proposed sample size estimates are 45 patients per group (it is estimated that up to 120 Veterans will be randomized in order to obtain the sample size of 45 participants per group).

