Blood samples for pharmacogenetics will be collected in one EDTA (purple top) vacutainer from each study patient at the baseline visit. All blood samples will be coded and stored in a -80 degree freezer at the Durham VAMC. When the study is closed to enrollment (end of Year 3, beginning of Year 4), all coded frozen blood samples will be transferred to Duke University's Center for Human Genetics for genotyping. SNP genotyping will be performed on Applied Biosystems' 7900HT Real-Time PCR System using both pre-developed and custom TaqMan® SNP Genotyping Assays.

The availability of potential neurosteroid biomarkers in serum combined with possible candidate gene data could lead to "population segmentation" approaches to optimal clinical care in patients with chronic pain receiving pregnenolone, providing the "right drug for the right patient" at the "right dose" (Breier 2005). These projects could also lead to the characterization of serum neurosteroid biomarkers and/or candidate genes that identify Veterans with chronic pain and comorbid disorders who are most likely to respond to an intervention with pregnenolone or other neurosteroid agents.

RISK/BENEFIT ASSESSMENT

Potential Risks

a) Physical Risk: Physical risks associated with participation in this study include the risks of drawing blood and adverse effects from the study medication. Possible side effects from drawing blood include bruising, bleeding or pain at the injection site, and (rarely) fainting and infection. Blood draws at each visit are minimal risk. In terms of the study medication, pregnenolone has been well-tolerated at doses up to 700 mg per day.

Side effects exceeding placebo that have occurred in previous clinical trials with pregnenolone conducted by [name], the applicant's primary mentor, have included mild restlessness, mild cold extremities, mild muscle pain/stiffness, and mild headache. If a subject develops side effects at any dose, they may be brought down to the previously tolerated dose or they may be withdrawn from the study and, as appropriate, referred for evaluation and treatment. We will perform laboratories at each study visit (Chem 7, CBC, GI Panel) and an ECG at study entry and completion. No serious adverse events have been reported to date utilizing pregnenolone (sold as a dietary supplement over-the-counter in the U.S.).

Of note, subjects will NOT be tapered from their current stable medication regimen; pregnenolone will only be "added on" to treatment-as-usual.

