b) Emotional Distress: Subjects may potentially experience emotional distress as a result of participating in this study. The study procedures could potentially lead to emotional distress from discussing trauma histories during mental health assessments. Each subject will be closely monitored for emotional distress, suicidal ideation and homicidal ideation at screening and each study visit. If a subject becomes significantly distressed or their psychiatric symptoms worsen and intervention is deemed appropriate, they will be walked to the emergency psychiatry clinic (on site) for evaluation and treatment (including potential hospitalization). The study medication will be discontinued and they will be withdrawn from the study if the patient is hospitalized, or if medical and/or psychiatric issues take precedence over study participation.

c) Safety Plan: We will implement a rigorous safety plan that encompasses close monitoring and care of medical issues in this study. The conduction of safety monitoring includes the following procedures outlined in the Physician On-Call Cascade (please see below in Adverse Event and Safety Evaluation section). This study would be conducted under FDA IND # 114,799. We will follow all FDA guidelines for annual progress, adverse event, and other reporting procedures for this outpatient randomized control trial.

Adequacy of Protection from Risks

Physical Risk and Subject Safety Possible side effects from drawing blood (as mentioned above) will be attended to as usual in the phlebotomy laboratory. If a subject experiences serious adverse effects from the study medication, it will be discontinued and s/he will be withdrawn from the study. The subject will immediately be referred for appropriate evaluation and treatment. All serious adverse effects will be documented and reported as required by the FDA and local IRB committee.

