Patients must have clinical diagnosis of chronic low back pain. Pain must be present on most days for at least 6 months. The pain must be either restricted to low back or associated with radiation to the proximal portion of the lower limb only (Class 1 and 2 per Quebec Task Force on Spinal Disorders). Study candidates must not have: a) neurological radicular signs; b) presumptive compression of a spinal nerve root on a simple radiogram (that is, spinal instability or fracture); or c) compression of a spinal nerve root confirmed by specific imaging techniques (computerized tomography [CT], myelography, or magnetic resonance imaging [MRI]) or other diagnostic techniques (for example, electromyography). The above diagnosis shall be made by a study physician and will be based on history, and physical and neurological examination. In addition, absence of spinal fracture, spondyloisthesis grade 3 or 4, tumor, abscess or acute pathology in the low back/abdominal regional must be confirmed by historical record of imaging studies (any of the following: plain x-ray, CT, or MRI). As per the study physician's opinion, there must be no clinically significant change in the condition since the time of imaging. A study physician will review medical charts and interview patients to determine disease criteria.

Pregnenolone: Pregnenolone is available over-the-counter and sold as a dietary supplement in the U.S., and estimated to be used by thousands of people. It has a very favorable side effect profile among clinical studies conducted to date; please see Appendix 3 for recent pregnenolone safety data summary. Despite its ubiquitous availability as a dietary supplement, pharmacokinetic data for pregnenolone are limited. Please see also summary of pregnenolone in the PDR for Nutritional Supplements (attached). No serious adverse events have been attributed to pregnenolone to date.

Treatment Compliance

Compliance for each visit interval is defined as taking between 80% and 120% of the study drug prescribed for that interval. For subjects who demonstrate noncompliance, the PI and/or study coordinator will counsel patients on the importance of study drug compliance and drug accountability. Patients who miss more than 6 consecutive doses of medication or are less than 80% compliant will be withdrawn from the study.

The following procedures will be employed to assure appropriate drug accountability:

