5. Subjects will return for a study visit every week (except for Week 5). Vital signs will be assessed at each visit. A member of the research team will ask subjects about possible side effects and adverse reactions (Adverse Event Form). Patients will be asked to return capsules of pregnenolone or placebo to determine compliance with study medication. The subject will then be given a new supply of capsules (either pregnenolone or placebo, depending upon random assignment) at Visits #3, #4, and #5. At baseline (Visit #1) and at the final visit (Visit #6), patients will receive a Chem 7, GI panel, CBC, TSH, prolactin, lipid panel, urine drug screen, and urinalysis; all patients will receive urinalysis and female patients will also receive a pregnancy test at all visits. Urine drug screens will be administered at Visits 1, 2, 4 and 6. A Chem 7, GI panel, and CBC will also be performed at Visits #2,3,4, and 5 (a Chem 7, GI panel, and CBC will therefore be performed at each study visit).
6. At Visits #1, 2, 3, 4, 5 and 6, three extra red-top tubes will be collected for determination of pregnenolone levels and pregnenolone metabolite levels. Serum will also be utilized for protein and other small molecule characterizations. At the end of these analyses, any remaining serum will be destroyed.
7. At Visit #1, two purple-top tubes and one PAX gene tube (blood RNA tube) will be collected for genetic analyses examining polymorphisms in the enzymes leading to neurosteroid synthesis and metabolism, as well as other candidate genes relevant to pathophysiology and treatment.
8. At Visit #6, patients will be instructed to taper the study medication by 100mg/day (for example, if the patient is taking 500mg of pregnenolone at Visit #6, the following day he will take 400 mg, the day after 300mg, etc. until the taper is complete).
9. At the final visit (Visit #6), patients will receive psychiatric assessments, vital signs, and side effect assessment. In addition, the physical exam and ECG will be repeated.
10. BPI, BDI, DTS, AIS, 36-item Short form Health Survey, selected BAC-A subtests, CDRS and CSSRS will be administered during each study visit. The Patient's Global Impressions of Improvement will be administered during Visits #3, #4, #5 and #6. The Roland Morris Scale and Fagerstrom Test for Nicotine Dependence (FTND) will be administered at Visit #1, #2 and #6. Please see schedule of events.

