11. All subjects who complete the entire study (6 visits total) will receive two follow-up phone calls during Weeks #7 and #8 and be asked about adverse events (Hillside Adverse Events) and suicidality (CSSRS).

ADVERSE EVENTS AND SAFETY EVALUATIONS

Adverse Events: Adverse events will be recorded by administration of the Hillside Adverse Event Form and reviewed by a study physician (please see physician study team schedule/cascade). Adverse events will be assessed at all study visits after the screening visit (i.e. Visits 2-6). In addition, adverse events will be assessed by a follow-up telephone call at the end of the study medication taper (Week 7) and again one week after study medication has been stopped (Week 8). In addition to receiving these regular adverse effect assessments, patients will be given a toll free study number that they can call if they have questions regarding the dose escalation schedule or medication side effects. They will also be provided with the cell phone number of the study PI, [name], PhD as well as [name], MD. Other covering VA physicians (as part of the call cascade) will be accessible to [name] as per the call schedule.

Suicidality Safety Procedures for Follow-Up Phone Calls:

If a participant reports suicidality (suicidal ideation, gesture, or attempt) as per the Columbia Suicide Severity Rating (CSSRS, which is an FDA-recommended assessment for suicidality in clinical trials) during any follow-up phone call, a study physician will be notified immediately to determine whether the situation requires immediate clinical intervention. If a participant is thought to be at imminent risk to self, he/she will be referred immediately to emergency psychiatric care at the Durham VA Emergency Department, to Psychiatric

Emergency Services (PEC) at the Durham VA, or to the participant's local Emergency Department for further evaluation. If the participant is unwilling or unable to get to emergency psychiatric care and appears to be in imminent danger of self-harm, the study team will contact local law enforcement who will follow up with the participant at their current location.

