Secondary analyses will include the following assessments. Assessment of changes in mood, anxiety, sleep, working memory, executive function, and pain interference (BDI, DTS, Tower of London, Digit Sequencing Task, BPI interference, PGI, AIS) will be analyzed via a repeated measures analysis similar to analyses for primary outcome assessments. Categorical analyses of patient response (30% improvement, 50% improvement) will be evaluated via a comparison of proportions using Fisher's exact test. Time to event analyses will also be performed, to examine the time to 30% and time to 50% reduction in 24 hour average pain score, using daily pain score data. These analyses will be performed by calculating Kaplan-Meier survival curves. Changes in physical function, mental health, cognitive symptoms and back pain-related disability will be assessed using ANCOVA models. Safety will be assessed by comparing the incidence of major and minor side effects (defined in human subjects section below) in the study drug vs. placebo groups, using Fisher's exact tests. Path analysis will be used to perform a preliminary assessment of whether any pain reduction effect is independent of possible effects of study drug on anxiety and mood.

Missing data: The mixed models used to evaluate the continuous response variables are able to handle moderate amounts of missing data provided they are missing at random. We will examine the missing at random

assumption by assessing differences between dropouts and completers on baseline as well as response variables up to point of premature withdrawal. If the missing at random assumption does not appear to be tenable, we will report the mixed models results but spend additional effort characterizing treatment effect at time of premature withdrawal.

[figure not shown]
Power Analysis and Sample Size Determination:

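### The week 7 and 8 adverse-event and suicidality calls are promised only to completers, so side effects are compared over unequal follow-up and early leavers have no stated study contact after stopping

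*Combined protocol and SAP*

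**What the plan says.** **Analysis.** Under Statistical Methods, among the secondary analyses: "Safety will be assessed by comparing the incidence of major and minor side effects (defined in human subjects section below". The comparison is pregnenolone against placebo by Fisher's exact tests. No time window, denominator or exposure adjustment is given. The missing-data paragraph concerns the mixed models for continuous responses.

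**Who is called.** Study Timeline, item 11: "All subjects who complete the entire study (6 visits total) will receive two follow-up phone calls during Weeks #7 and #8". On those calls they will "be asked about adverse events (Hillside Adverse Events) and suicidality (CSSRS").

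**Who leaves early.**
- Potential Risks, a) Physical Risk: patients with side effects at any dose are handled so that "they may be brought down to the previously tolerated dose or they may be withdrawn from the study".
- Potential Risks, b) Emotional Distress: "The study medication will be discontinued and they will be withdrawn from the study if the patient is hospitalized". The same applies if medical or psychiatric problems take priority.
- Adequacy of Protection from Risks: serious adverse effects lead to stopping the drug and withdrawal.
- Treatment Compliance: "Patients who miss more than 6 consecutive doses of medication or are less than 80% compliant will be withdrawn from the study".

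**What follows withdrawal.** The risk sections provide clinical referral and reporting of serious adverse effects. Table 1 has no early-termination column.

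**The concern.** Fisher's test treats each patient as simply having or not having the effect, however long that patient was observed. Here the observation time depends on completion, and non-completion is partly a matter of tolerability. If more patients leave on pregnenolone, its side effects are counted over less time and the drug can look safer than it is.

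The second stake is individual safety. The plan asks patients who tolerated treatment about suicidality after drug stops, but does not assign those questions to patients withdrawn for psychiatric worsening. The Purpose section itself says chronic pain raises suicide risk. These answers cannot reliably be recovered later.

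**Working it through.** **The plan's own figures.** The documents give no figure for the safety comparison. The efficacy sample size reproduces: 45 per group, difference 0.6, SD 1.0 and two-sided alpha 0.05 give power 0.804 by the exact t calculation. Research Design and Methods says "it is estimated that up to 120 Veterans will be randomized in order to obtain the sample size of 45 participants per group". That is at most 120 - 90 = 30 leavers, or 30/120 = 25%.

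**Observation time.** Randomised drug starts at Visit 3 (week 2).
- Completer: last call at week 8, so 8 - 2 = 6 weeks.
- Leaver at Visit 4 (week 3): 1 week. Leaver at Visit 5 (week 4): 2 weeks.

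**Model.** Take a background complaint with the same true six-week risk B in both arms, a constant hazard, and leaving unrelated to the complaint. With N per arm, L leavers and w weeks observed in leavers:

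observed incidence = [(N - L) x B + L x (1 - (1 - B)^(w/6))] / N

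B, L, w and the arm splits are assumptions; none is in the documents. The table shows pregnenolone minus placebo in percentage points. The true difference is 0.

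| N per arm | Leavers, placebo vs pregnenolone | w | B = 30% | B = 50% | B = 70% |
|---|---|---|---|---|---|
| 45 | 3 vs 6 | 1 | -1.6 | -2.6 | -3.5 |
| 45 | 3 vs 6 | 2 | -1.3 | -2.0 | -2.5 |
| 60 | 10 vs 20 | 1 | -4.0 | -6.5 | -8.6 |
| 60 | 10 vs 20 | 2 | -3.1 | -4.9 | -6.2 |
| 60 | 15 vs 15 | 1 or 2 | 0 | 0 | 0 |

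Worked cell (N = 60, 10 vs 20, w = 1, B = 50%): a leaver's observed risk is 1 - 0.5^(1/6) = 10.9%.
- Placebo: (50 x 0.5 + 10 x 0.109)/60 = 43.5%.
- Pregnenolone: (40 x 0.5 + 20 x 0.109)/60 = 37.0%.
- Difference: -6.5 points.

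**How much is due to the calls?** Remove the calls for everyone, so completers are observed for 4 weeks with risk 1 - 0.5^(4/6) = 37.0%. The gap is then (20 - 10)/60 x (37.0 - 10.9) = 4.3 points. So 4.3 of the 6.5 points is ordinary early dropout. Across the unequal rows that share is 53% to 71%.

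**How much would extra calls recover?** A call at the end of dosing and another a week later take a Visit 4 leaver from 1 to 2 weeks. The gap moves from 6.5 to 4.9 points, a gain of 1.6.

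**What a rate would do.** Patient-weeks are 50 x 6 + 10 x 1 = 310 on placebo and 40 x 6 + 20 x 1 = 260 on pregnenolone. At the weekly hazard ln(2)/6 = 0.1155, expected events (allowing recurrence) are 35.8 and 30.0, which is 0.1155 per patient-week in both arms. Under a constant hazard, the rate removes the distortion that the calls leave behind.

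**The case against.** **The calls may already cover everyone.** The general paragraph under Adverse Events and Safety Evaluations describes both calls without limiting them to completers. But it times the first at the end of the taper in week 7, and Study Timeline item 8 places the taper late: "At Visit #6, patients will be instructed to taper the study medication by 100mg/day". The numbered procedure names completers. At best the text is ambiguous.

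**Other safeguards exist.** Dose reduction is allowed instead of withdrawal. There is a toll-free number, on-site emergency psychiatry, referral and serious-event reporting. These protect patients in part, but the toll-free line relies on the patient to call, and none collects the adverse-event form or suicidality scale after withdrawal. Part of the safety section, and the human subjects section cited for the definitions of major and minor side effects, were not in the text available to me. A follow-up rule there would change the conclusion.

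**A patient withdrawn for a side effect is already counted.** This stands. Later silence cannot lower the count for that class, so the model describes other complaints and other leavers.

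**Thirty leavers is the upper reading.** This stands too. Experimental Design has 90 randomised after the lead-in, and Subject Recruitment has up to 120 enrolled to reach 90. Exclusion criterion 11 removes poor diary-keepers up to Visit 3. Much of the loss may precede randomisation.

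**Three stronger readings are not supported.** A reader might infer that a sizeable effect of stopping is being hidden; the documents give no rate for one, and Physical Risk lists only mild effects. A reader might infer that all leavers stop abruptly; at 100 mg/day the next 100 mg taper step is zero, so this concerns only those leaving from 300 mg/day or more. A reader might infer that the comparison is bound to favour pregnenolone; that needs more leavers on pregnenolone, which nothing in the documents shows.

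**Conclusion.** The point holds as a follow-up gap with a modest, conditional effect on the safety comparison. As written, the plan collects no study adverse-event or suicidality data after early withdrawal, and its incidence comparison mixes about 6 weeks of observation with 1 or 2.

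The distortion between arms is about 1.3 to 3.5 points with 45 per arm and 3 vs 6 leavers. It reaches 8.6 only with 60 per arm, 10 vs 20 leaving at Visit 4 and a 70% background risk, and it is zero if leaving is equal. These sizes assume the event rates, arm splits and a constant hazard. If complaints cluster in the first week or two, the loss is smaller. More than half of the distortion would exist without any calls, so the main reason to extend them is the lost information on patients who stopped early. This is a worthwhile, inexpensive improvement to a pilot study. It does not affect the sample size or primary analysis.

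**What to change.** 1. **Study Timeline, item 11.** Offer both calls, with the Hillside form and the suicidality scale, to every patient who took randomised drug, including those who stop early. Time them at the end of dosing (or of any taper) and one week later. Align the general adverse-event paragraph, and add a sentence to the consent form.
2. **Statistical Methods, safety analysis.** Keep the major and minor classes and Fisher's tests. Add events per patient-week observed by arm. Report withdrawals for side effects, and patients not reached by the calls, by arm.

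**Cost.** Table 1 allows 10 minutes per call. At the upper reading, 30 leavers x 2 calls x 10 minutes = 600 minutes, about 10 staff hours, with no extra visits or blood draws. Some leavers will decline or not be reached, so the gap narrows but does not close.

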Experimental Design: The proposed design is a randomized, double-blind, two-arm trial of pregnenolone and placebo to determine the possible analgesic effects in OEF/OIF Veterans with chronic low back pain. The total study duration is 8 weeks (6 study visits followed by two-follow up phone calls). All patients will monitor pain symptoms for one week with pain diaries, followed by a 1-week placebo-only lead-in period, 90 subjects will be randomly assigned to one of two groups. Of these subjects, 45 subjects will receive pregnenolone, and 45 subjects will receive placebo for 4 weeks (in addition to the taper period of 5 days). Patient interview assessments and laboratory studies will be performed at each interview time point. Pregnenolone, allopregnanolone and other neurosteroid metabolites will be determined by gas chromatography / mass spectrometry (GC/MS), proceeded by high performance liquid chromatography (HPLC). Those subjects randomized to pregnenolone will receive this neurosteroid on the following schedule:

- Pain symptom monitoring with pain diaries for 1 week, then
- Placebo lead-in phase 0 mg in two doses (0 mg, PO, BID) for 1 week, then
- Pregnenolone 100 mg in divided doses (50 mg, PO, BID) for 1 week, then
- Pregnenolone 300 mg in divided doses (150 mg, PO, BID) for 1 week, then
- Pregnenolone 500 mg in divided doses (250 mg, PO, BID) for 2 weeks.

Dosing: Pregnenolone fixed escalating up to 500mg/day will consist of the following schedule:

Visit 1 (week 0, screening visit) and pain symptom assessment

Visit 2 (week 1) placebo lead-in (all participants)

Visit 3 (week 2, baseline visit): 50mg PO, BID x 1 week,

Visit 4 (week 3): 150mg PO, BID x 1 week,

Visit 5 (week 4): 250mg PO, BID for two weeks.

Visit 6 (week 6): No medication will be dispensed; study medication will be tapered by 100mg per day and then discontinued. The FDA has reviewed this protocol and issued an Investigational New Drug number (IND #114,799) for this randomized controlled trial utilizing the pregnenolone doses above for low back pain, and has provided a formal permission to proceed letter for this study. In addition, [name] (the PI's primary mentor on this VA funded Career Development Award) currently holds FDA IND numbers for the use of pregnenolone for treatment of schizophrenia (IND #71,768), PTSD (IND #73,099) and TBI (IND #78,270).

Methodology for Neurosteroid Identification and Quantification:

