Any incident regarding theft/loss of data, authorized access of sensitive data or storage devices or non-compliance with security controls will be addressed according to VA policy (VHA Handbook 1200.05, 10j; 1058.01 11.a; 6500, Appendix D and 6500.2) and will be reported to Durham VAMC PO and ISO immediately using the following: [contact].

Study members who are initially part of the study team, but leave the study team for whatever reason will no longer have access to participant study data.

DATA ANALYSIS AND STATISTICAL CONSIDERATIONS

Statistical Methods

Analysis of treatment effects will use the mixed-models approach to repeated-measures analysis of variance (SAS Institute, Cary, NC) with baseline and endpoint scores as dependent variables, time as a within-subject repeated measure, and treatment group (pregnenolone or placebo) as a between-subjects fixed factor. The primary analyses for this will be based on an intention-to-treat principle that will include in the analyses all randomized subjects. The primary efficacy outcome variable is the weekly mean of the average pain scores (0 – 10 numeric rating pain score recorded daily from patient) after study drug initiation. These are obtained over time, and thus we will use mixed effects models with random intercepts to account for subject effects and the correlation among repeated measurements within a subject. Models will be developed which include as independent variables the treatment group and the baseline pain score. Thus, the effect of the intervention will be assessed by examining the significance of the slope β_1 coefficient for intervention in the following model:

$$P_{it} = \beta_0 + b_{0i} + \beta_1 Int + \beta_2 BaseP + \beta_3 t + e_{it}$$

where P_{it} is the mean weekly pain score for the i^{th} individual at time point t , β 's denote fixed effects, b_{0i} is the random intercept for the i^{th} individual, and e 's are random errors. Patients who are withdrawn from the study because of side effects will only be included in outcome assessments in which they participated. The mixed effects models can handle incomplete panels of information. All tested hypotheses will be considered statistically significant if the 2 sided p value is ≥ 0.05 unless otherwise specified.

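### The planned check of missing-at-random cannot show whether it fails, and no analysis tests how far the result depends on unseen pain scores

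*Combined protocol and SAP*

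**What the plan says.** The Missing data paragraph (Data Analysis and Statistical Considerations) describes the mixed models as "able to handle moderate amounts of missing data provided they are missing at random". It will examine the missing-at-random "assumption by assessing differences between dropouts and completers on baseline as well as response variables up to point of premature withdrawal". The consequence is stated next: "If the missing at random assumption does not appear to be tenable, we will report the mixed models results but spend additional effort characterizing" how treatment was doing when the patient left.

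On the primary model, Statistical Methods says: "Models will be developed which include as independent variables the treatment group and the baseline pain score". The equation adds time and a random intercept. All randomised subjects are analysed, and those withdrawn for side effects contribute only the assessments they attended.

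Three other places bear on the point:

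- **Treatment Compliance:** "Patients who miss more than 6 consecutive doses of medication or are less than 80% compliant will be withdrawn from the study".
- **Study Timeline, item 10:** "BPI, BDI, DTS, AIS, 36-item Short form Health Survey, selected BAC-A subtests, CDRS and CSSRS will be administered during each study visit".
- **Expected loss:** no dropout rate is given. Research Design and Methods says "it is estimated that up to 120 Veterans will be randomized in order to obtain the sample size of 45 participants per group", Experimental Design says "90 subjects will be randomly assigned to one of two groups", and Subject Recruitment speaks of up to 120 being enrolled.

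The documents contain no delta adjustment, tipping point, reference-based imputation, selection model or pattern-mixture model.

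**The concern.** The plan treats a comparison on observed data as a test of MAR and makes its only follow-up depend on the outcome. The comparison cannot do that job.

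- If dropouts differ from completers on baseline pain or earlier weekly pain, that is evidence against missing completely at random (MCAR). MAR allows such differences, and the primary model already conditions on those scores.
- If they do not differ, nothing has been learned about the scores that were never recorded. Those scores are what MNAR is about.

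So a flag can cast doubt on a sound result, and a pass can give false reassurance. The fallback does not repair this: it is triggered by the same comparison, uses data only up to withdrawal, and leaves the MAR model as the reported result.

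The comparison does have a proper use, which is to find predictors of dropout that lie outside the primary model, such as depression, trauma, insomnia and BPI scores or adherence. The plan attaches no such action to it.

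**Working it through.** **Inputs.** From Power Analysis and Sample Size Determination: difference 0.6, SD 1.0, two-sided alpha 0.05, 45 per group. From Experimental Design: four weeks of treatment, hence four weekly scores after drug initiation.

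**The plan's own figure.** An exact two-sample t-test gives 80.4% power at 45 per group and 79.5% at 44, so 45 reproduces.

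**Loss.** If 120 are randomised to obtain 90, loss is 1 − 90/120 = 25%. If 90 are randomised, as Experimental Design says, it may be much lower. Both 25% and 10% are shown.

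**1. What unseen scores can do (arithmetic).** If imputed scores in one arm are shifted by δ points, the treatment coefficient moves by m × δ, where m is that arm's share of missing weekly scores: m = loss × (mean weeks missing ÷ 4).

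- 25% loss: m runs from 0.25 × 1/4 = 0.0625 to 0.25 × 4/4 = 0.25. With losses spread evenly, m = 0.25 × 2.5/4 = 0.156. One point of δ therefore moves the effect by 10% to 42% of 0.6.
- 10% loss: m runs from 0.025 to 0.10.
- Numerical check with 15 of 60 lost per arm, spread evenly: shifts of 0.156 (active) and 0.157 (placebo) per point.
- Opposing shifts of 2 points: 2 × 0.156 + 2 × 0.157 ≈ 0.63, which cancels 0.6.
- To lose significance from 0.60 with standard error 0.11 (from the simulation below): (0.60 − 1.96 × 0.11) ÷ 0.156 ≈ 2.5 points of combined opposing shift, ignoring added imputation variance.
- A plain unadjusted end-of-treatment comparison of 60 per arm is more fragile. Its critical difference is 1.98 × √(2/60) = 0.36, so a one-arm shift of about (0.60 − 0.36) ÷ 0.25 ≈ 0.95 points suffices at 25% loss, and about 2.4 points at 10%.

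**2. Simulation of the model and the check.** Assumptions not in the documents: 60 per arm, within-subject correlation 0.6, constant true effect 0.60, monotone dropout. The dropout hazard is logistic in the last observed score (MAR) or the current unseen score (MNAR), with log-odds slopes 0.5 and 1.0 per point. There were 1,000 trials per scenario, fitted with the plan's random-intercept model. The check was taken as any p<0.05, because the plan states no rule. Pooled: baseline or week-1 score. Within arm: baseline or last observed score, in either arm.

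Results at 25% loss:

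| Dropout pattern | Estimate, slope 0.5 / 1.0 | 95% CI coverage | Flagged, pooled | Flagged, within arm |
|---|---|---|---|---|
| MAR | 0.601 / 0.602 | | 54–96% | 78–100% |
| MNAR, both arms alike | 0.598 / 0.597 | | 41–88% | 56–93% |
| MNAR, placebo only | 0.567 / 0.548 | | | |
| MNAR, active only | 0.629 / 0.653 | | | |
| MNAR, placebo high and active low | 0.540 / 0.495 | 91.5% / 82.7% | 8–12%* | 45–90%* |
| MNAR, placebo low and active high | 0.660 / 0.699 | 90.7% / 83.0% | * | * |
| MCAR | | | 9% | 21% |

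*Range over both opposite-direction patterns. Blank cells are not reported here.

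- At 25% loss and matched slope, harmless MAR was flagged more often than every MNAR pattern, including the one-arm patterns.
- With no true effect, the placebo-low and active-high pattern at slope 1.0 rejected in 15% of trials instead of 5%.
- At 10% loss every estimate stayed within 0.55 to 0.64, yet harmless MAR was still flagged 30% / 70% of the time pooled (slopes 0.5 / 1.0).
- Separately written code reproduced the estimates to within about 0.02.

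**3. A different check rule.** This used correlation 0.5, no true effect, 25–27% dropout after week 2, Bonferroni-corrected t-tests at baseline and weeks 1 and 2, and 400 runs. MAR was flagged in 100% of runs with no bias (type I error 4.5%). MNAR in both arms was flagged in 4.8%. MNAR in the active arm only was flagged in 6.5%, with bias of 0.074 toward benefit and type I error 11.5%.

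**The case against.** The logic is not in dispute; the argument is about weight.

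- **The comparison may already cover outside variables.** The plan's reference to response variables can be read to include the BDI, DTS, AIS and BPI scales. That is fair. What is missing is any action that brings them into a model, and adherence is not covered.
- **The flag rates rest on an invented rule.** The plan leaves tenability to judgement, and the rates vary widely: MNAR alike in both arms is flagged 41–93% of the time in one set-up and 4.8% in the other. This stands for the percentages. The argument follows from the definitions and does not need them.
- **25% is the least favourable reading.** Inclusion criterion 3 (baseline pain) and exclusion criterion 11 (diary completion before Visit 3) could account for much of the attrition from 120 to 90 before randomisation. This stands.
- **Daily diaries may capture the worsening that leads to withdrawal.** When the model was allowed to see the triggering week, every 25%-loss pattern at slope 1.0 returned 0.60–0.61 with about 95% coverage. That is the favourable extreme; partly observed weeks fall between.
- **Cancelling 0.6 needs an extreme corner.** With losses spread evenly, a 2-point shift in one arm moves the estimate by 0.31 and leaves 0.29, still above 1.96 × 0.11 = 0.22. This stands.
- **It is a four-week pilot.** True, but it is powered at 80% for an efficacy test at 0.05, and its result will be read as evidence.

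These points limit the size. None makes the check informative or supplies the missing analysis.

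**Conclusion.** The concern holds. The check cannot distinguish MNAR from MAR, the only follow-up depends on it, and nothing planned shows how sensitive the result is to unseen scores. This conclusion rests on the definitions and on the plan's text, not on simulation assumptions.

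The size does rest on assumptions about loss, correlation and mechanism. Bias is nil under MAR or when MNAR is alike in both arms, about 0.03 to 0.05 when one arm is affected, and up to about 0.10 when the arms are affected in opposite directions at 25% loss. Because the mixed model is reported either way, the practical harm is mainly misinterpretation. The change should be made, but it does not invalidate the primary analysis.

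**What to change.** Amend the statistical section as follows.

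1. State that MAR cannot be tested from observed data.
2. Keep the comparison of dropouts and completers, by arm, as a description of dropout predictors. Where predictors lie outside the primary model (for example BDI, DTS, AIS, BPI or adherence), add a supportive analysis that includes them in a multiple-imputation model for weekly pain.
3. Keep the mixed model under MAR as primary.
4. Pre-specify one MNAR sensitivity analysis, run whatever the comparison shows: delta-adjusted multiple imputation of weekly scores after withdrawal. Vary delta separately in each arm, for example from −2 to +2 points (twice the planning SD) in 1-point steps. Report the treatment coefficient and its 95% CI over the grid, and the tipping point if the primary result is significant. The range is a suggestion; what matters is that it is fixed in advance. Placebo-reference imputation is optional.

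The cost is revised wording, standard imputation code and one 5 × 5 table, with no new data and no extra patients. The drawback is a little more analysis work, and readers must judge which deltas are plausible.
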